A Comparative Analysis between Articulated and Conventional Stubby Prostheses

September 27, 2016

[name]

Study Protocol

A 10 meter walk test will be administered on a level sound surface and a gravel surface. The test will take place under four different conditions; 1) stubby prosthesis on level surface 2) stubby prosthesis on gravel surface 3) sidekick prosthesis on level surface 4) sidekick prosthesis on gravel surface. Each trial will be performed 3 times and the completion times will be averaged. There will be a 2-minute break between each 10-meter test and a 30-minute break when changing the feet style. During the 30-minute break the participant will change from the conventional stubbies to the sidekicks and the proper resistance will be set. The participant will be given about 20 minutes to rest and 10 minutes to walk around with the new feet style. The participant will walk a total of 10 meters. The intermediate 6 meters will be measured to allow for acceleration and deceleration. The participant will be instructed to walk at a comfortable, leisure speed.

A gravel surface will be constructed using a tarp and gravel. This surface will be used as an uneven surface in comparison to a level ground surface for the 10 meter walk test.

The TUG test will be performed on just the level surface using a standard chair with arm rests. The participant will begin seated in a chair. A piece of tape is placed 3 meters away, clear for the participant to see seated in the chair. On the word "GO" the participant will stand up, walk to the line on the floor, turn around and sit back in the chair. Time will be recorded from the word "GO" until the participant are seated, with the participant's back firmly against the chair. The participant will be wearing the G-Walk technology to analyse the movement at the pelvis. Three trials will be performed using each foot type and the participant will receive a 5 minute rest between the individual trials and a 10 minute rest between the foot change.

The G-walk technology is a Bluetooth wireless system that is worn around the waist with an ergonomic belt allowing the participant to move freely without any restrictions.

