A comparative analysis between College Park Sidekick Feet and conventional stubby prosthesis.

NCT02921295

Sep 27, 2016

Statistical Plan

A two-way analysis of variance (ANOVA) as a between subject variable and within subject variable will be used to analyze the dependent variable, completion time in seconds. A secondary analysis will observe additional dependent variables: cadence, velocity, step length, stride length, and pelvic girdle angles. The independent variables being analyzed include stubby feet compared with the Sidekicks and a level surface compared to gravel. The two-way ANOVA is used to determine whether there are any significant differences between the mean values of the independent groups. If a significant difference is detected an unpaired t-test will be implemented to determine if statistical significance exists. A probability value of 0.05 will be set at the level of statistical significance. Statistical analysis will be performed on SPSS software. The balance confidence scale and RPE scale will be compared across independent variables.

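### Surface order is not controlled: level is listed before gravel for both feet, and if that list is followed the surface effect cannot be separated from practice or fatigue

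*Protocol*

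**What the plan says.** The Study Protocol text introduces the 10-metre walk test with "The test will take place under four different conditions" and numbers them: "1) stubby prosthesis on level surface 2) stubby prosthesis on gravel surface 3) sidekick prosthesis on level surface 4) sidekick prosthesis on gravel surface". Within each foot, level comes before gravel. On repeats and rest it says "Each trial will be performed 3 times and the completion times will be averaged" and "There will be a 2-minute break between each 10-meter test and a 30-minute break when changing the feet style".

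The only order stated in prose is that of the feet: "During the 30-minute break the participant will change from the conventional stubbies to the sidekicks and the proper resistance will be set". At that change, "The participant will be given about 20 minutes to rest and 10 minutes to walk around with the new feet style". The surface used for this familiarisation walk is not given.

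The Statistical Plan says that a two-way ANOVA "will be used to analyze the dependent variable, completion time in seconds", and "The independent variables being analyzed include stubby feet compared with the Sidekicks and a level surface compared to gravel". It names no order, period or sequence term. Neither document mentions randomising, rotating, counterbalancing or recording the order in which surfaces are walked.

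**The concern.** In a repeated-measures comparison, a factor whose levels are always met in the same order carries any practice or fatigue effect with it. The numbering puts gravel after level for both feet, and the prose on the foot change agrees with the numbering (items 1 and 2, then 3 and 4), so a tester could well run the session as listed.

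Two results of the planned ANOVA would then be affected. The first is the surface main effect, which the SAP plans to test. The second is the foot-by-surface interaction, which a two-way ANOVA normally reports and which would show whether any difference between the feet depends on the ground. If everyone has the same surface order, adding an order term cannot help, because order and surface are then the same variable within each foot.

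**Working it through.** The documents state no sample size, SD, effect size or drift, so there is no planned figure to reproduce. The check is what the ANOVA contrasts pick up if the list is followed.

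**Inputs.** From the protocol: four conditions in slots 1 to 4 (stubby/level, stubby/gravel, Sidekick/level, Sidekick/gravel), three walks each, so 4 × 3 = 12 walks. Assumed: a slot effect s1 to s4 in completion time (negative for practice, positive for fatigue) that adds to the true cell mean.

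**Bias in each contrast.**
- Surface (gravel minus level) = (s2 + s4 − s1 − s3)/2
- Interaction = (s4 − s3) − (s2 − s1)
- Foot (Sidekick minus stubby) = (s3 + s4 − s1 − s2)/2

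**Illustrations, all with assumed drift.**

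| Drift pattern | Slot effects | Surface | Interaction | Foot |
|---|---|---|---|---|
| Steady, d per slot | d, 2d, 3d, 4d | d | 0 | 2d |
| Differs by foot | 0, −0.1, 0, −0.3 s | −0.2 s | −0.2 s | −0.1 s |
| Common, diminishing (first gain = 1 unit) | 0, −1, −1.5, −1.75 | −0.625 | +0.75 | −1.125 |

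- Row 1: surface (2d + 4d − d − 3d)/2 = d; interaction d − d = 0; foot (3d + 4d − d − 2d)/2 = 2d.
- Row 2: surface (−0.1 − 0.3)/2 = −0.2; interaction −0.3 − (−0.1) = −0.2; foot (−0.3 + 0.1)/2 = −0.1.
- Row 3: surface (−1 − 1.75 − 0 + 1.5)/2 = −0.625; interaction −0.25 − (−1) = +0.75; foot (−1.5 − 1.75 − 0 + 1)/2 = −1.125.

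Rows 2 and 3 are different mechanisms. Steeper learning on the second foot pushes the interaction negative. One learning curve that flattens over the session pushes it positive, with no difference between feet in how people learn.

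**If the list is not followed strictly.** Suppose a fraction p of participants walk level first, under steady drift. Level-first participants are shifted by +d and the rest by −d, so the surface bias is pd − (1 − p)d = (2p − 1)d. It is d at p = 1 and 0 at p = 0.5. With no record of order, p is unknown.

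**With surface order balanced in each foot block.** Both stubby cells receive (s1 + s2)/2 and both Sidekick cells (s3 + s4)/2. Surface and interaction biases are 0 in all three rows; foot bias is unchanged (2d, −0.1 s, −1.125).

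**With foot order balanced as well (four sequences).** Under a common drift, each cell occupies each slot equally often. In row 3 every cell receives (0 − 1 − 1.5 − 1.75)/4 = −1.0625, so all three biases are 0.

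**The case against.** The strongest reply is that the numbered items describe a 2 × 2 layout and are not a schedule. That is fair as far as it goes. A reader might infer that every participant walks level and then gravel, but the protocol calls the items conditions and never states a surface sequence. The finding must therefore stay conditional. It does not disappear, because a protocol silent on order permits a fixed one and would leave no record of what was done.

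Second, both document titles describe a prosthesis comparison, and no interaction hypothesis is stated. This limits the importance of the point. Surface is nonetheless a named independent variable for completion time.

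Third, the walks are short and at an easy pace, with rest between them and rest plus familiarisation at the foot change. These provisions may well reduce fatigue and early learning. They do not separate surface from position.

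Fourth, the three repeats could reveal drift within a condition if individual times are kept. The plan averages them, and carrying that drift across conditions would require an assumed form.

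Two stronger readings also fail. A reader might infer a direction for the interaction bias, but the two plausible mechanisms above have opposite signs. A reader might also want an inflated false-positive rate for surface. That would need a sample size, a bias and a true surface effect of zero, none of which the documents supply. If gravel really does slow walking, practice would shrink the difference and fatigue would enlarge it.

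**Conclusion.** The point stands in conditional form. Surface order is neither specified nor controlled, and running the plan as listed would confound surface with position. Under steady drift the surface bias is d, the drift per condition, and the interaction is unaffected. The interaction is biased whenever the level-to-gravel drift differs between the two foot blocks, whether because people learn differently on each foot or because a shared drift is non-linear. These results assume that drift adds to the cell means; the values in the table show mechanism and do not estimate the bias in this trial.

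This is a design weakness worth correcting before testing begins, because a fixed order cannot be repaired in the analysis. It is distinct from the foot-order problem, which the prose states more firmly and which carries twice the bias (2d) under steady drift.

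**What to change.** Add to the protocol: *Within each foot block, half the participants walk level first and half gravel first, from a prepared randomised list; the order used is recorded.* If foot order is also counterbalanced, use the four sequences formed by foot order and surface order.

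Include order in the ANOVA if the sample size allows. Balance alone removes the bias, but under steady drift it leaves half the participants' surface contrasts shifted by +d and half by −d, which adds d² to the variance of that contrast. Fitting order takes this out. It costs 1 between-subject degree of freedom with two surface orders, or 3 with four sequences, so it should be optional while the sample size is unknown.

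No extra walks, surfaces or equipment are needed. The tester must follow a list. Balancing surface order alone does nothing for the foot-order confounding, which needs its own change.

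### The 10-metre walk is written with stubbies always first and Sidekicks always second, so the foot effect cannot be separated from practice, fatigue or first exposure to the test gravel

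*Protocol*

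**What the plan says.** The Protocol's 10-metre walk test numbers its four conditions with both stubby conditions ahead of both Sidekick conditions: "1) stubby prosthesis on level surface 2) stubby prosthesis on gravel surface 3) sidekick prosthesis on level surface 4) sidekick prosthesis on gravel surface". The foot change is described in one direction only: "During the 30-minute break the participant will change from the conventional stubbies to the sidekicks and the proper resistance will be set". Familiarisation is written only for the second foot type: "The participant will be given about 20 minutes to rest and 10 minutes to walk around with the new feet style". On repetition, the Protocol says "Each trial will be performed 3 times and the completion times will be averaged". On rest, it says "There will be a 2-minute break between each 10-meter test and a 30-minute break when changing the feet style".

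The SAP's main outcome is completion time, analysed by a two-way ANOVA. Its factors are foot type and surface: "The independent variables being analyzed include stubby feet compared with the Sidekicks and a level surface compared to gravel". It names no order, period or sequence term. Neither document mentions randomising or counterbalancing the order, or a group that starts in Sidekicks.

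For the TUG, the Protocol gives three trials per foot type and the rests between them, but no foot order.

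**The concern.** If everyone walks in stubbies first, being in Sidekicks and being in the second block are the same thing. A participant who speeds up because the test has become familiar improves the Sidekick times. A participant who tires worsens them. The comparison of foot types, which is the purpose of the study, would then rest on a contrast that mixes the device with the order of testing.

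The gravel raises a further problem. It is built for the test, and under this order it is first met in stubbies. If people learn to walk on it, the gain appears on gravel in the Sidekick block and much less on level ground. The analysis would show that as a foot-by-surface interaction in favour of Sidekicks, even if the two feet behaved alike.

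The 10-minute walk-around adds another difference between the blocks, because no equivalent is written for the stubby block.

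**Working it through.** The plan gives no sample size, SD, effect size or power, so there is no figure of its own to reproduce.

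**Exposure before the first timed Sidekick walk.** Inputs from the Protocol: 2 surfaces, 3 repetitions per condition, 10 m per walk.
- Walks in stubbies: 2 × 3 = 6, of which 3 are on gravel.
- Distance walked: 6 × 10 m = 60 m. Only the middle 6 m of each walk is timed, so 6 × 6 m = 36 m is measured.

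**What the contrast estimates.** Let F be the true Sidekick-minus-stubby effect and P the second-minus-first-block effect.
- Order as written: mean Sidekick time minus mean stubby time = F + P for every participant. The bias is P, that is, 100% of the block effect.
- Half of participants in each order: the difference is F + P in those starting in stubbies and F − P in those starting in Sidekicks. The average is [(F + P) + (F − P)] / 2 = F.
- Interaction: if the block effect is P_L on level ground and P_G on gravel, the foot-by-surface contrast under the written order is (F_G − F_L) + (P_G − P_L). Learning specific to gravel enters it directly.

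**Can a model separate F from P?** The design matrix has columns for participant, foot, block, surface and foot × surface. With 10 assumed participants that is 10 + 4 = 14 columns.

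| Order | Foot–block correlation | Rank |
|---|---|---|
| Stubbies always first | 1.00 | 13 of 14 |
| Half start in each foot | 0.00 | 14 of 14 |

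Under the written order, a block term added to the ANOVA cannot be estimated alongside foot, and more participants do not change that.

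**What this could do to the error rate.** Assume F = 0, a two-sided paired t-test at 0.05 (the SAP does not state sidedness), and a block effect of d SDs of the within-person difference. The test statistic is noncentral t with n − 1 degrees of freedom and noncentrality d√n. For n = 10 and d = 0.5, the noncentrality is 0.5 × √10 = 1.58, the critical value is 2.262, and the rejection probability is 29.3%.

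| Block effect d (assumed) | n = 6 | n = 10 | n = 20 |
|---|---|---|---|
| 0 | 5.0% | 5.0% | 5.0% |
| 0.25 | 8.0% | 10.9% | 18.6% |
| 0.5 | 17.1% | 29.3% | 56.5% |
| 1.0 | 50.7% | 80.3% | 98.9% |

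**After counterbalancing.** A simulation of the period-adjusted two-sequence analysis used 200,000 replicates, n = 6, 10 and 20, and d = 0, 0.5 and 0.8. Bias in the foot effect was about 0 and the type I error was 0.049 to 0.051. This assumes carryover does not differ between the two orders.

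**The case against.** **The order is inferred.** No sentence says that the sequence is fixed for everyone, and the numbered list could be read as a plain list of conditions. That is fair for the list, and the surface order within each foot type rests on the list alone. The sentence on the foot change is different: it sets out a procedure, in one direction, and no other sequence appears anywhere.

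**The Protocol already limits block effects.** It has 2-minute breaks, about 20 minutes of rest at the change, a walk-around in the second foot type, averaged trials and a self-chosen pace. These may well reduce fatigue and unfamiliarity. They do not remove learning of the test or of the gravel, and the data could not show whether they had worked.

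**The error rates are not those of the planned analysis.** This stands. The table is for a correct paired test, while the SAP follows its ANOVA with an unpaired t-test. At d = 0.5 and n = 10, a simulated unpaired test rejects about 32%, 12% and 1% of the time for assumed within-person correlations of 0, 0.5 and 0.8. Across n = 6 to 20 the range is about 1% to 59%. Low rates here come from a test that ignores the pairing; the bias in the estimate is unchanged.

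**The direction is unknown.** This also stands. Practice and fatigue pull opposite ways, and the interaction favouring Sidekicks is one plausible outcome, not a prediction. Trial-level times could show trends within a block, but carrying them across the 30-minute break needs assumptions that the data cannot test.

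**Some exposure is undocumented.** The documents do not say whether the TUG precedes the walk test, or how used participants are to stubbies or to everyday gravel. None of this breaks the tie between foot type and block.

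**Conclusion.** The concern holds for the 10-metre walk test and should be settled before data collection. Followed as written, the foot comparison carries 100% of an unknown block effect, and neither the SAP's model nor any reanalysis of a single-sequence design can take it out. A null result is affected as much as a positive one, because fatigue could hide a real benefit.

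The aliasing depends on no assumed number, only on the described sequence being applied to all participants. The false-positive rates depend on assumed n, an assumed block effect and a paired test, and should be read as illustration. The conclusion does not extend to the TUG, where the foot order is simply not stated.

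**What to change.** In the Protocol:
- Randomise the first foot type 1:1 in small blocks, so that half the participants start in Sidekicks.
- Counterbalance the surface order between participants, and keep it the same for both foot types within a participant.
- Write the same walk-around period before both foot blocks.
- Record the order actually used.

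In the SAP, add block (first or second) as a fixed effect in a within-subject model, and state the assumption that carryover does not differ between orders. A block term without the change of order would not help.

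Optionally, state the TUG foot order and use the same one, ideally within the same foot block so that only one change is needed. The main fix does not depend on this.

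The cost is a short randomisation list, about 10 more minutes per participant for the first-block walk-around, and one error degree of freedom. At n = 10 the critical t rises from 2.262 (9 df) to 2.306 (8 df), and 2.306 / 2.262 = 1.02, about 2%. No extra participants, staff or equipment are needed.

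### Four of the five secondary gait and pelvic variables have no stated source on gravel, although the SAP names level versus gravel as a factor; the TUG has no analysis suited to its paired design

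*Protocol*

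**What the plan says.** **SAP, Statistical Plan.** A two-way ANOVA "will be used to analyze the dependent variable, completion time in seconds". The next sentence adds five secondary variables: velocity, cadence, step length, stride length and pelvic girdle angles. The sentence after that gives the factors as foot type (stubby or Sidekick) and surface (level or gravel), without exempting any outcome. The only pairwise test is an unpaired t-test, used if a significant difference is found. The TUG is not mentioned.

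**Protocol, 10-metre walk.** This is the only test done on both surfaces. On what is recorded, the protocol says "Each trial will be performed 3 times and the completion times will be averaged" and "The intermediate 6 meters will be measured to allow for acceleration and deceleration". Of the gravel it says "This surface will be used as an uneven surface in comparison to a level ground surface for the 10 meter walk test". No sensor is mentioned in these paragraphs.

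**Protocol, TUG.** "The TUG test will be performed on just the level surface using a standard chair with arm rests". Here the sensor is assigned: "The participant will be wearing the G-Walk technology to analyse the movement at the pelvis". On repetition: "Three trials will be performed using each foot type".

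**Protocol, closing G-Walk paragraph.** It describes a wireless device "worn around the waist with an ergonomic belt allowing the participant to move freely without any restrictions", and names no test, surface or output variable.

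**The concern.** The SAP appears to want a foot-by-surface comparison of gait and pelvic variables. The protocol places the instrument that would supply pelvic data, and perhaps the step data, only in a test that is never done on gravel.

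Staff work from the protocol. If the belt is not worn during the walks, those data do not exist and cannot be recovered later. The trial would then lose the surface comparison for most of its secondary variables, including whether any difference between foot types changes on uneven ground.

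A related gap is that TUG data will be collected with both foot types, while the SAP gives no analysis that suits them.

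**Working it through.** No sample size, power or effect figure is stated, and none is needed. The check matches each SAP variable to the test, surface and instrument that the protocol states for it.

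| SAP variable | Stated source, level | Stated source, gravel |
|---|---|---|
| Completion time (primary) | 10-metre walk | 10-metre walk |
| Velocity | derivable from walk time | derivable from walk time |
| Pelvic angles | TUG, if its pelvic movement recording is taken to give them | none |
| Cadence | none explicit | none |
| Step length | none explicit | none |
| Stride length | none explicit | none |

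**Velocity.** Velocity = 6 m / time on either surface, if the middle 6 m is what is timed. The protocol says that this stretch is measured and does not use the word timed, so this is an assumption, though a natural one.

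**The other four.** Write S for Sidekick and C for the conventional stubby, with subscripts L and G for level and gravel.

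- Surface effect = ½(S_G + C_G) − ½(S_L + C_L). Both gravel means are missing.
- Foot-by-surface interaction = (S_G − C_G) − (S_L − C_L). The first bracket is missing.
- Foot effect on level ground = S_L − C_L. This needs no gravel data. For pelvic movement it is available from the TUG. For cadence, step length and stride length it is available only if the TUG recording is assumed to yield them.

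**Trials per participant.** Walks: 2 foot types × 2 surfaces × 3 repetitions = 12, of which 2 × 3 = 6 are on gravel. TUG: 2 foot types × 3 trials = 6. Sensor wear is stated for the TUG trials and is not addressed for the walks.

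**TUG analysis.** Surface has only one level in the TUG, so the two-way model cannot be fitted to it. The SAP's remaining test is unpaired and follows a significant ANOVA. Each participant does the TUG with both foot types, so the two sets of results come from the same people and call for a within-participant comparison.

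**The case against.** The strongest reply is that this is silence and not contradiction. The walk paragraph names no instrument at all, not even a timer, so leaving out the G-Walk there is weak evidence that it is not worn. The closing G-Walk paragraph stands apart from the TUG text. The protocol is also not a full inventory of measurements: the SAP refers to a balance confidence scale and an RPE scale that the protocol never mentions. All of this is fair. A reader might infer that the sponsor decided against wearing the sensor on the walks, and the documents do not support that. What stands is that neither document instructs it, and the SAP's comparison depends on it.

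Second, the ANOVA sentence is tied to completion time, and the link between the secondary variables and surface rests on sentence order. That is correct. Applying both factors to all outcomes is the natural reading, but it is an inference.

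Third, a reader might infer that the primary outcome is undefined, because the SAP does not say which test its completion time comes from and the protocol times both the walk and the TUG. The documents largely answer this. The protocol speaks of completion times only for the walk, and only the walk has a gravel condition, so a foot-by-surface analysis must refer to it.

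Fourth, a reader might conclude that cadence, step length and stride length certainly have no source even on level ground. That goes too far. The sensor's stated purpose is pelvic movement, but the documents do not say what else it outputs.

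Finally, the choice of a paired test for the TUG is a separate matter from the missing data source. It is raised here because the fallback below relies on TUG data, and it adds no weight to the main point.

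**Conclusion.** The point holds for the secondary analysis. Four of the five secondary variables (cadence, step length, stride length, pelvic angles) have no stated gravel source, so with both documents followed as written their surface and foot-by-surface effects cannot be estimated. At most, a level-ground foot comparison from the TUG remains. Primary walk time is unaffected, and velocity is obtainable on both surfaces if the middle 6 m is the timed distance.

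The conclusion rests on two readings: that the SAP's factors apply to the secondary variables, and that the protocol's single wearing instruction is taken literally. If the sensor was always meant to be worn on the walks, the defect is in the wording only, but it still needs correcting before data are collected. The TUG point is smaller: its data currently have no suitable planned analysis.

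This should be fixed. It does not put the main comparison in doubt.

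**What to change.** **(a) Data source.** State in the protocol that the G-Walk is worn on all twelve 10-metre walks, with both foot types and on both surfaces. Name those walks as the source of cadence, step length, stride length and pelvic angles. The level-ground values should come from the walks and not from the TUG: the TUG includes standing up, turning and sitting, so setting TUG level data against gravel walk data would mix test with surface. Confirm at the same time that the middle 6 m is the timed distance.

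If sensor use on the walks is not feasible, limit the surface factor in the SAP to walk time and velocity, and report pelvic movement from the TUG only as a level-ground comparison of foot types. Drop any of the other three variables for which no recording exists.

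**(b) TUG.** Add the TUG to the SAP, and analyse TUG time and TUG pelvic movement with a paired, within-participant comparison of the two foot types.

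**Cost.** About two sentences in the protocol and two in the SAP. The existing belt sensor must be available for the walks, and twelve extra recordings per participant must be processed. The protocol does not say whether the walks and the TUG share a session, so availability of the sensor is an assumption to confirm.
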